The primary effectiveness endpoint, achievement of hemostasis within 5 minutes, will be investigated by a 2-sided test for non-inferiority using logistic regression, taking into account the following covariates: study center, surgery type (cardiothoracic, general or vascular), and initial bleeding severity (mild or moderate). Non-inferiority of CELSTAT to Surgicel will be assessed using the confidence-interval approach and a non-inferiority margin of 10%.

The difference in the proportion of subjects having postoperative rebleeding during study participation will be performed using the same logistic regression model described for the primary efficacy endpoint.

Secondary Endpoints

The logistic regression model used for the primary endpoint will also be performed on the proportions of subjects with hemostasis achieved at 3, 7, and 10 minutes after treatment application, and on the proportion of subjects with intraoperative rebleeding from the TBS after achievement of hemostasis.

The TTH will be presented by Kaplan-Meier curves. In addition, a log-rank test will be performed to assess the difference between the distributions of TTH for CELSTAT and Surgicel.

Descriptive statistics will be generated for the secondary safety endpoints (AEs, clinical laboratory parameters and vital signs). Shift tables will be generated for laboratory parameters.

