9. STUDY DESIGN

9.1 Brief Summary

This is a prospective, randomized, controlled, single-blind pivotal trial of CELSTAT as an adjunct to hemostasis for the treatment of mild to moderate bleeding in subjects undergoing cardiothoracic, general and vascular surgery. The study is to evaluate the effectiveness and safety of CELSTAT vs active control in 258 subjects. It will be conducted at approximately 26 sites in the United States (20) and Europe (6).

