9.5 Factors Influencing the Outcome

Surgery type (cardiothoracic, general and vascular) and bleeding severity (mild, moderate) may potentially influence hemostatic effectiveness. Therefore, these factors will be considered in the analysis.

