9.6 Randomization and Blinding

9.6.1 Randomization

Subjects will be randomly assigned to CELSTAT or Surgicel at a ratio of 1:1. Randomization will be stratified by study center and surgery types (cardiothoracic, general, vascular surgery). It is aimed to achieve a similar distribution of the 3 surgery types in the randomized study population. This will be controlled via an interactive Web-response system (IWRS), [REDACTED] (USA), using dynamic allocation. Within [REDACTED], a capping strategy will be used to ensure equal allocation of randomized subjects across surgical types. On the day of surgery, upon confirmation of preoperative eligibility criteria, a member of the site study staff other than the surgeon will obtain a treatment assignment (CELSTAT or Surgicel) from the IWRS. To keep the surgeon blinded until an eligible TBS has been identified for study treatment, adequate amounts of each study product (CELSTAT and Surgicel) will be taken into the operating room for potential use of one of them as the study treatment.

Immediately after the subject's intraoperative eligibility for study treatment has been confirmed (ie, an eligible TBS with Grade 1 or 2 bleeding has been identified), the assigned treatment will be revealed to the surgeon and the assigned device will be applied to the TBS. Following surgery, the treatment assignment and the actual treatment applied will be entered in the electronic case report form (eCRF) for the subject.

If the subject's eligibility is not confirmed pre- or intraoperatively, the subject's operation will be performed according to hospital standards. The study site designee will enter the date and reason(s) for the subject's exclusion in the eCRF.

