13.4 Methods of Analysis

13.4.1 Primary Outcome Measures

The primary efficacy analysis will be carried out on the PPS. The analysis using the FAS will be used as a supportive analysis.

The primary efficacy parameter is defined as follows: The primary endpoint is set to success if hemostasis is achieved at 5 minutes after the treatment application and is maintained until surgical closure. If hemostasis is not achieved at 5 minutes, if additional hemostatic treatment other than study device is required, or if intraoperative rebleeding occurs, the primary endpoint will be set to “treatment failure”.

The primary effectiveness endpoint will be investigated by a 2-sided test for non-inferiority using the confidence-interval (CI) approach to compare the CELSTAT group to the Surgicel group. A non-inferiority margin of 10% (the largest clinically acceptable difference) will be used; thus, if the lower bound of the 2-sided 95% CI (based on normal approximation) around the difference in proportions (CELSTAT group - Surgicel group) is greater than -10% in the final analysis, CELSTAT will be declared non-inferior to Surgicel.

The specific hypotheses of the risk difference to be tested are as follows:

$$H_0: P_{\text{CELSTAT}} - P_{\text{Surgicel}} \leq -\delta$$

$$H_1: P_{\text{CELSTAT}} - P_{\text{Surgicel}} > -\delta$$

where

P_{CELSTAT} = the proportion (%) of subjects achieving hemostasis by 5 minutes in the CELSTAT group,

P_{Surgicel} = the proportion (%) of subjects achieving hemostasis by 5 minutes in the Surgicel group, and

δ = the non-inferiority margin of 10%.

Additionally, if the lower bound of the 2-sided 95% CI is larger than zero, superiority of CELSTAT versus Surgicel will be claimed.

The null hypothesis will be tested against the alternative using logistic regression, taking into account the following covariates: study center, surgery type (cardiothoracic, general or vascular) and initial bleeding severity (mild or moderate).

The primary safety analysis, of the difference in proportion of subjects rebleeding from the TBS requiring surgical re-exploration during the subject's study participation, will be performed using the same logistic regression model described for the primary efficacy endpoint.

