13.4.2 Secondary Outcome Measures

The logistic regression model used for the primary analysis will also be performed for the following secondary endpoints:

- The difference in proportion of subjects having achieved hemostasis at 3 minutes and which is maintained until surgical closure
- The difference in proportion of subjects having achieved hemostasis at 7 minutes and which is maintained until surgical closure
- The difference in proportion of subjects having achieved hemostasis at 10 minutes and which is maintained until surgical closure

- The difference in proportion of subjects with intraoperative rebleeding from the TBS after achievement of hemostasis

The TTH will be presented by Kaplan-Meier curves. In addition, a log-rank test will be performed to assess the difference between the distributions of TTH for CELSTAT and Surgicel.

AEs that occurred during or after treatment application will be presented in summary tables. Summary tables shall indicate the number of subjects who experienced AEs. In addition, tables will be prepared to list each AE, the number of subjects in each treatment group who experienced an AE at least once, and the rate of subjects with AEs. AEs grouped by MedDRA system organ class and preferred term will be presented by severity grade (mild, moderate, severe) and relatedness to treatment (“possibly related” or “probably related” AEs will be considered “related”; “unlikely related” or “not related” AEs will be considered “not related”).

All AEs for each subject, including the same event on several occasions, will be listed, giving both MedDRA preferred term and the original term used by the investigator, system organ class, severity grade, seriousness, relation to the treatment, onset date, and stop date.

AEs that occurred before the start of treatment application will be listed separately.

Clinical laboratory parameters and vital signs will be summarized by visit and treatment group. Shift tables will be generated for laboratory parameters.

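### The primary logistic model lists study center at about 26 sites of about 9 evaluable subjects and is not linked to the deciding CI; with one fixed term per site it would miss the stated 2.5% error

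*Protocol*

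**What the plan says.** Protocol 13.4.1 sets the null and alternative on the risk-difference scale with a margin of 10 percentage points. Its criterion for declaring non-inferiority concerns a lower confidence limit: "the 2-sided 95% CI (based on normal approximation) around the difference in proportions (CELSTAT group - Surgicel group) is greater than -10" percent. That sentence names no covariates. Further down, the section says: "The null hypothesis will be tested against the alternative using logistic regression, taking into account the following covariates: study center", followed by surgery type and initial bleeding severity.

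The synopsis (section 4) puts the two statements next to each other. The endpoint "will be investigated by a 2-sided test for non-inferiority using logistic regression", and then "Non-inferiority of CELSTAT to Surgicel will be assessed using the confidence-interval approach". Section 13.4.2 says "The logistic regression model used for the primary analysis will also be performed for the following secondary endpoints", and the endpoints it lists are differences in proportions. Section 13.4.1 also reuses the model for the primary safety endpoint.

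On center, section 9.6.1 says "Randomization will be stratified by study center and surgery types". Section 9.5 names surgery type and bleeding severity, not center, as factors that may influence hemostasis, and says "Therefore, these factors will be considered in the analysis". Sections 9.1 and 10 plan about 26 sites with roughly equal recruitment. Section 13.1 gives 121 evaluable and 129 randomized subjects per group, one-sided error 2.5% and power 80%.

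**The concern.** The hypotheses concern a difference in proportions, but a logistic treatment coefficient is a log odds ratio. A conversion step is needed before the model can test a 10-point margin, and the protocol does not say that the deciding CI is the result of one. The covariate list is itself fixed in the protocol, and it includes a factor with about 26 levels.

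Entered in the usual way, as one indicator per site, center would use up most of the model's coefficients in a trial where failures are few. The pivotal claim rests on one lower bound, and a model-based standard error that is too small moves that bound in favour of the new device.

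**Working it through.** **Inputs.** 121 evaluable per group, 242 in total; one-sided error 2.5%; power 80%; margin 10 points (13.1). About 26 sites, roughly equal (9.1, 10). The planning success rates are blacked out, so the rates below are assumptions. For orientation, the pilot had 51/55 and 24/27 successes at 5 minutes (7.3.2).

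**The plan's own figures.** 121/0.95 = 127.4, so 128, and the next multiple of 3 is 129, as stated. The 121 cannot be confirmed without the rates, but it is plausible. With 89% Surgicel and 90% CELSTAT, n = (1.960 + 0.842)² × (0.89×0.11 + 0.90×0.10)/(0.01 + 0.10)² = 122.

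**Scale.** The odds ratio equivalent to −10 points depends on the Surgicel rate:
- 85%: (0.75/0.25)/(0.85/0.15) = 0.53
- 90%: (0.80/0.20)/(0.90/0.10) = 0.44
- 95%: (0.85/0.15)/(0.95/0.05) = 0.30

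**Sparsity.** Evaluable subjects per site: 242/26 = 9.3. With one term per site the model has 1 intercept + 1 treatment + 2 surgery type + 1 severity + 25 center = 30 coefficients. At 90% success there are 242 × 0.10 = 24 failures. The expected number of sites with no failure is 26 × p^(242/26):
- p = 0.85: 26 × 0.220 = 5.7
- p = 0.90: 26 × 0.375 = 9.8
- p = 0.95: 26 × 0.620 = 16.1

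The chance of at least one such site, 1 − (1 − p^(242/26))^26, is 99.8% or more in all three. Those sites have no finite center estimate. At the margin with Surgicel at 90% and CELSTAT at 80%, average success is 85%, so the 5.7 applies.

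**Error at the margin.** The raw CI was enumerated exactly at 121 per arm (strata 40/40/41, constant odds ratio giving an average difference of −10 points). The two model CIs are risk differences standardised from the logistic fit with delta-method standard errors. They were simulated with 60,000 trials per case, 26 sites of 9 to 10 subjects, arms balanced within site, no site effect, and an assumed severity odds ratio of 2 (none in the first case). Monte Carlo error is about 0.1 point.

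| Surgicel rate by surgery type | Raw CI | Model without center | Model, one term per site |
|---|---|---|---|
| 90/90/90% | 2.82% | 2.9% | 3.6% |
| 85/90/95% | 2.65% | 2.8% | 3.7% |
| 80/92/98% | 2.23% | 2.7% | 3.8% |
| 75/96/99% | 1.64% | 2.7% | 4.4% |

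With an assumed site SD of 0.5 on the logit scale (first three cases), the error is 3.7, 3.8 and 3.9% with site terms and 2.7, 2.7 and 2.5% without center. A separate 6,000-trial run of the first case gave 3.5% with site terms. A coarser run of 1,500 trials per case, with no surgery-type effect, gave 3.5, 3.4 and 2.9% at Surgicel rates of 90, 85 and 80%; its Monte Carlo standard error is √(0.03×0.97/1500) = 0.4 point.

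**Mechanism.** In that coarser run at 90% versus 80%, the mean model standard error with site terms was 0.0427 against an empirical SD of 0.0470. Without center the figures were 0.0452 and 0.0465.

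**Does the choice matter?** The raw CI and the model with one term per site gave opposite verdicts in 4.4 to 10.4% of trials at equal rates and in 1.0 to 3.0% at the margin. For the raw CI against the model without center the figures are 1.4 to 5.4% and 0.3 to 1.2%.

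**Reuse for safety.** At an assumed re-exploration rate of 1 to 5%, 258 subjects yield 2.6 to 12.9 events, and 26 × (1 − r)^(258/26) gives 23.5 down to 15.6 sites with none.

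**The case against.** The decision rule is explicit: only one sentence declares non-inferiority, and it fixes scale, margin, CI level and direction. A reader might infer two rival decision rules. The documents do not support that. The synopsis runs model and CI together as one analysis, and 13.4.2 applies the model to differences in proportions, so the model-based reading is favoured. The missing link is mainly a clarification, and how a risk difference is derived from a logistic fit is normally left to the SAP.

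A reader might also infer that the primary error is inflated as planned, or that the model cannot yield a result. Neither follows. No section says that center enters as one fixed term per site, so pooling or a random effect stays open. At sites without failures the standardised risk difference remains finite, and the harm is a standard error that is too small. If the raw CI decides, sparsity does not reach the primary verdict.

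Nor do the figures condemn the raw CI. Its error is close to nominal or conservative, and the adjusted model without center has no lower error in any of the four cases. Its power gain at equal rates runs from 0 to about 4.6 points and depends on the assumed surgery-type spread.

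All of this stands. What it leaves is that the protocol itself fixes center in the covariate list without qualification, at a number of sites where the usual coding does not hold the stated error.

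**Conclusion.** The point holds conditionally and is worth fixing. If the logistic model supplies the deciding CI and center is entered as one fixed term per site, the one-sided error at the margin is about 3.5 to 4.4% instead of 2.5%, and at least one site without a failure is almost certain. If either condition fails, this inflation does not arise; with the raw CI the error is about 1.6 to 2.8%. The excess is moderate, roughly 1 to 2 points, and was smaller (2.9%, in the coarse run) at an assumed Surgicel rate of 80%. All of it rests on assumed success rates, about equal site sizes and the assumed surgery-type and severity effects described above. The lack of a stated link between model and CI is the lesser part. It matters because it leaves open whether the sparse model decides.

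**What to change.** In 13.4.1 and the synopsis, name one computation as the source of the deciding 2-sided 95% CI for the risk difference, and call the other supportive. Two workable examples are a risk difference standardised from the logistic model with treatment, surgery type and bleeding severity, and a risk difference stratified by surgery type. The documents do not force a particular estimator.

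State that 26 separate center terms will not be entered. Either pool small sites by a rule fixed in advance, or adjust for center only in a sensitivity analysis. Apply the same handling wherever the model is reused, that is, for the primary safety endpoint (13.4.1) and the secondary endpoints (13.4.2).

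The cost is a few sentences and slightly more analysis work. No new data are needed, because surgery type and bleeding severity are already recorded, and the sample size need not change for this. The downside is that the primary model then reflects the center stratification factor only partly or not at all. A small normal-approximation excess (about 2.7 to 2.9% in the model without center) also remains.

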7.3.2 Prior CELSTAT Clinical Investigation

The sponsor conducted a pilot clinical study (Study 621101) to evaluate the safety and effectiveness of CELSTAT (brand name Traumastem in the study report) as an adjunct to hemostasis for tissue bleeding in subjects undergoing open cardiac, intraabdominal (including retroperitoneal) or pelvic surgery as compared to Surgicel. This was a prospective, randomized, positive-controlled, subject-blinded, multicenter study.

In eligible subjects, the study treatment was applied at the TBS after conventional surgical hemostasis was completed. The number and size of layers of device used was at the discretion of the surgeon. The investigational device did not need to be removed and could be left in situ.

All 82 subjects enrolled achieved hemostasis at the primary TBS within 10 minutes. At 5 minutes after the start of device application hemostasis was achieved in 51 of 55 subjects (93%) in the CELSTAT group and in 24 of 27 subjects (89%) in the Surgicel group. Median time to hemostasis (TTH) in the CELSTAT group was 117 seconds, compared with 158 seconds in the Surgicel group.

The proportion of subjects with any adverse event (AE)/adverse device effect (ADE) was similar for the CELSTAT and Surgicel groups, with 74.5% (41/55 subjects) and 74.1% (20/27 subjects), respectively. Only 3 AEs/ADEs (postprocedural hematoma, postprocedural complication, and liver abscess) in the Surgicel group, all occurring in 1 subject, were considered by the investigator to be related to study treatment.

The pilot study defined AEs/ADEs of special interest as any of the following:

- Postoperative rebleeding
- Infection: signs included fever $>100^{\circ}\text{F}$ or $>37.8^{\circ}\text{C}$ after the first 48 hours with malaise and or lethargy
- Hematoma at the surgical site

- Change in coagulation parameters (as noted by change from normal or abnormal without clinical significance, respectively, at baseline to abnormal or abnormal with clinical significance at Day 7 (± 1)/Discharge (Visit 3): prothrombin time, activated partial thromboplastin time, platelet count
- Increased wound healing time (more than 2 weeks) or wound dehiscence
- Foreign body reactions and allergic reactions (to device and material); signs of inflammation or encapsulation
- Embolization (especially vascular surgeries) and associated complications

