9.4.1.2 Safety

The primary safety outcome measure is postoperative rebleeding from the TBS requiring surgical re-exploration during the subject's study participation.

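### The primary safety comparison is tied to a multi-covariate logistic model whose ordinary treatment estimate does not exist if an arm has no event; for effectiveness, the same model is not linked to the risk-difference null it is said to test

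*Protocol*

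**What the plan says.** **Primary safety.** Section 9.4.1.2 defines the endpoint: "The primary safety outcome measure is postoperative rebleeding from the TBS requiring surgical re-exploration". Section 13.4.1 frames the analysis as a difference in proportions and says it "will be performed using the same logistic regression model described for the primary efficacy endpoint". The Synopsis agrees: "The difference in the proportion of subjects having postoperative rebleeding during study participation will be performed using the same logistic regression model". Neither place gives an expected rate, a margin, a success rule or an alternative for few events.

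**Effectiveness.** Section 13.4.1 writes the hypotheses as a risk difference with a 10-point margin. It declares non-inferiority "if the lower bound of the 2-sided 95% CI (based on normal approximation) around the difference in proportions" lies above -10%. It then adds: "The null hypothesis will be tested against the alternative using logistic regression, taking into account the following covariates: study center, surgery type" and initial bleeding severity. The Synopsis says the endpoint "will be investigated by a 2-sided test for non-inferiority using logistic regression, taking into account the following covariates: study center" and the other covariates, and its next sentence keeps the confidence-interval approach with the 10% margin.

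**Secondary endpoints.** Section 13.4.2 extends the model: "The logistic regression model used for the primary analysis will also be performed for the following secondary endpoints". These include hemostasis at 10 minutes maintained to closure.

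**The concern.** Two features of the safety plan do not fit together. The target is a difference in proportions, but a logistic model's treatment coefficient is a log odds ratio. The model also needs events in both arms before ordinary maximum likelihood returns a finite coefficient. Re-exploration for rebleeding at one treated site, in mild to moderate bleeding, may well be rare, and the protocol offers no figure to the contrary. With center as a fixed factor the model has about 30 parameters: intercept 1, treatment 1, centers 25, surgery type 2, severity 1. The study may therefore reach its end with no usable output from the analysis prescribed for one of its two primary endpoints.

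For effectiveness the issue is narrower. One null hypothesis is given two methods on different scales, with no odds-ratio margin and no conversion between them.

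**Working it through.** **Inputs.** 129 randomized and 121 evaluable per group (Section 13.1); about 26 sites (Section 9.1); margin 10 points, one-sided alpha 2.5%, power 80% (Section 13.1). The assumed success rates are blacked out. Pilot (Section 7.3.2): one postprocedural hemorrhage among 55 CELSTAT and one among 27 Surgicel subjects, so 2/82 = 2.4%, Clopper-Pearson 95% CI 0.3% to 8.5%. Whether either needed re-exploration is not stated.

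**The plan's own numbers.** 121/0.95 = 127.4, rounded up to 128; the next multiple of 3 is 129, as stated. The 121 cannot be reproduced exactly without the rates but is attainable: 90% against 89% gives (1.96 + 0.842)² × (0.90×0.10 + 0.89×0.11)/0.11² = 121.9, so 122.

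**Safety: chance of an empty arm.** With a common event rate r, one arm has no event with probability q = (1 - r)^129, and at least one arm is empty with probability 1 - (1 - q)². Expected events are 258r.

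| Assumed rate | Expected events | q | At least one arm empty |
|---|---|---|---|
| 0.5% | 1.3 | 0.524 | 77% |
| 1% | 2.6 | 0.273 | 47% |
| 2% | 5.2 | 0.074 | 14% |
| 2/82 | 6.3 | 0.041 | 8.1% (8.5% if the rate is rounded to 2.4%) |
| 3% | 7.7 | 0.020 | 4% |
| 4% | 10.3 | 0.005 | 1% |

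A linear-programming separation check was run on 4,000 simulated trials per rate, with 26 near-equal centers as fixed effects, arms balanced within center, surgery type in thirds and severity 50/50. The full model had no finite treatment coefficient in 84%, 56%, 19%, 5% and 1% of trials at 0.5%, 1%, 2%, 3% and 4%. Without center it failed in exactly the empty-arm trials. The empty arm is therefore the main cause, and the center term adds to it.

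**Safety: an interval that survives.** The Miettinen-Nurminen score CI for CELSTAT minus Surgicel, 129 per arm:
- 0 vs 3 events: -6.6 to +0.6 points
- 0 vs 0 events: -2.9 to +2.9 points
- 3 vs 3 events: -4.6 to +4.6 points

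**Effectiveness: scale of the margin.** The odds ratio equal to a 10-point deficit is [(p - 0.10)/(1.10 - p)] / [p/(1 - p)]. At Surgicel success p = 84%, 89% and 93% this is 0.54, 0.46 and 0.37. No single odds ratio represents the margin, and the usual test of OR = 1 is not the stated null.

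**The case against.** **The protocol never says maximum likelihood.** Penalized or exact logistic regression would fit its wording, and an analysis plan that is not shown may choose one. That is fair, and it is why the claim is limited to the ordinary estimate. It does not settle the scale: the stated contrast is a difference in proportions, and no logistic coefficient is one.

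**The comparison need not vanish.** If the model is used to produce a risk difference, one empty arm still gives a finite answer. For 0/129 vs 3/129 without covariates it is -2.3 points, with a delta-method CI of about -4.9 to +0.3. This stands as a limit on the claim. That interval is narrower than the score CI, and it collapses to zero width at 0 vs 0.

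**The rate is assumed.** At the only figure the document offers, an arm is empty in about 8% of trials. The true rate may be lower, because the pilot figure counts hemorrhage rather than re-exploration, but the protocol does not establish that.

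**Hemostasis at 10 minutes.** A reader might infer that the same failure is built into this endpoint, since in the pilot "All 82 subjects enrolled achieved hemostasis at the primary TBS within 10 minutes". The documents do not support that. Section 13.4.2 requires hemostasis maintained until closure, and the pilot sentence does not count later rebleeding before closure. The 0/82 therefore does not fix the failure rate. At 121 per arm an arm without failures occurs in 50.5% of trials at a 1% failure rate but in only 5.0%, 1.4% and 0.4% at 3%, 4% and 5%.

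**Effectiveness.** A reader might infer that the non-inferiority test has no valid rule. It has one: Section 13.4.1 and the Synopsis both keep the confidence-interval approach. In simulation, the plain CI and a standardized risk difference from the adjusted model gave different verdicts in roughly 2% to 7% of trials. Both estimators are defensible, so this shows only that the choice should be fixed in advance.

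**Conclusion.** The point holds for primary safety. The protocol assigns a sparse event, with a risk-difference target, to an adjusted logistic model that can fail to return an ordinary treatment estimate. How often depends on an unstated rate: an arm is empty in about half of trials at 1%, about 8% at 2/82 and about 1% at 4%. This assumes equal rates and 129 treated per arm; fewer treated subjects would make it more frequent. The consequence is bounded. No margin or success rule uses this analysis, and rebleeding is also recorded as an adverse event and counted by arm, so the loss is the planned comparison and not a trial verdict.

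For effectiveness the point is minor: the text links a log-odds model to a risk-difference null without a conversion, although a usable decision rule is present. For 10-minute hemostasis, the documents support no more than a precaution in case failures turn out few.

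**What to change.** **Primary safety (Synopsis and Section 13.4.1).** Replace the logistic model with the number and proportion of subjects with an event per arm, and the difference CELSTAT minus Surgicel with a two-sided 95% Miettinen-Nurminen score CI (or an exact CI). The cost is an unadjusted comparison, which loses little with so few events, and a conservative interval at very low rates: enumerated coverage at 129 per arm is 99.6% at 0.5%, 97.7% at 1% and 95.5% to 95.6% at 2% to 4%. At unequal rates of 2% and 5% it is 94.2%.

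**Hemostasis at 10 minutes (Section 13.4.2).** The same CI may be used if failures are few.

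**Effectiveness (Synopsis and Section 13.4.1).** Name one risk-difference 95% CI as the sole basis for the non-inferiority verdict, and delete the statement that the logistic regression tests the null. The sponsor chooses between two options:
- The plain normal-approximation CI already written, with the logistic model supportive. At 121 per arm its exact power is 0.824 at 87% vs 84%, 0.803 at 90% vs 89% and 0.805 at 91.6% in both arms (illustrative rates). Its one-sided error at the margin is 2.6%, 2.8% and 3.0% at Surgicel success of 84%, 89% and 93%. If surgery type matters, it gives up about 1 to 3.5 points of power against an adjusted risk difference (simulated).
- A standardized risk difference from the adjusted model, with its CI. This keeps the adjustment that Section 9.5 calls for and that matches the stratified randomization, but the protocol must then state how it is computed and how center enters.

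All of this is wording; 121 and 129 per group need not change.
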